5.4.3 Exploratory Efficacy Endpoints

5.5 Safety Analyses

The Safety Population will be used for the safety analyses. The summary statistics for the main period will be done by starting dose and overall for all study visits and by cycle of exposure (as appropriate), unless specified otherwise. Descriptive summary will be generated for data collected during the LTE period as needed.

Patient data listings will be listed by starting dose, patient, dose level and study visit or start date of event if applicable, indicating on-treatment period or LTE on-treatment period.

In addition to standard analyses of all adverse events, dose limiting toxicities, laboratory tests, ECG data, and vital signs, the analyses of safety will include the following endpoints:

- 1) Percentage of participants receiving rescue medication at each dosing level and overall
- 2) Proportion of patients with an Intensity Grade 2 or higher bleeding event at each dosing level and overall
- 3) Bleeding scale (ITP Bleeding Assessment Tool [ITP-BAT]) at the end of treatment period for each dosing level and overall

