# 10.10 Safety and Tolerability Analysis

The incidence, severity, and relationship of TEAEs, laboratory tests, rescue treatment usage, and vital signs will be summarized descriptively. Qualitative safety data will be summarized by frequencies and percentages at each dose level, using the time boundaries of that dosing level (Part A only). Quantitative safety data will be summarized by descriptive statistics (arithmetic mean, standard deviation, median, minimum, and maximum) at each dose level (Part A only) and overall for Part B. Summaries will also be presented for the change from baseline, when

15 May 2024 Version number: 1

appropriate. The proportion of patients with a Grade 2 or higher bleeding event will also be summarized. Non-TEAEs will be described in separate listings.

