# 10.10.3 *Vital Signs*

Vital signs data will be presented by individual listings. Systolic blood pressure values <90 or >140 mmHg and diastolic blood pressure values <60 or >80 mmHg will be flagged as outside the normal range. Resting heart rate <40 or >100 beats per minute will be flagged as outside the normal range. Descriptive statistics of values and changes from baseline (mean, median, standard deviation) will be reported for quantitative variables separately for each dosing level, using the time boundaries for that level in Part A and overall in Part B. In addition, tabular and graphical summaries will be used, as appropriate.

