# 10.10.4 Rescue Medication, DLTs, and Bleeding Scale Scores

The percentage of patients receiving rescue medication at each dosing level (Part A only) and at any time during dosing for Part A, and at any time during dosing for Part B.

15 May 2024

Version number: 1

The percentage of patients with a DLT will be summarized at each dosing level, overall for Part A, and overall for Part B.

Bleeding scale (IBLS) scores will be summarized over time at each dosing level, overall for Part A, and overall for Part B.

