3.4.4 Analysis Visits

In addition to study visits described above, analysis visits based on dosing cycle of each dose level will be derived for descriptive summary during the main treatment period as follows:

- 1st Cycle of Exposure: Day 1, Day 8, Day 15 and Day 22
- 2nd Cycle of Exposure: Day 1, Day 8, Day 15 and Day 22
- 3rd Cycle of Exposure: Day 1, Day 8, Day 15 and Day 22
- 4th Cycle of Exposure: Day 1, Day 8, Day 15 and Day 22
- 5th Cycle of Exposure: Day 1, Day 8, Day 15 and Day 22
- 6th Cycle of Exposure: Day 1, Day 8, Day 15 and Day 22
- Xth Cycle of Exposure: Day 1, Day 8, Day 15 and Day 22 for patients who had treatment cycle(s) beyond Cycle 6
- Last value on-treatment (Last post-baseline visit during the main on-treatment period including unscheduled visits within each dose level)

For example, if a patient received 200 mg QD at Cycle 1, 400 mg QD at Cycle 2 and Cycle 3 and 300 mg BID at Cycle 4 and Cycle 5, the scheduled visits will be mapped to the analysis visits as follows:

Dose Level	Scheduled Visit	Analysis Visit
200 mg QD	Cycle 1 – Day 1, 8, 15 and 22	200 mg QD: 1st Cycle of Exposure – Day 1, 8, 15 and 22
400 mg QD	Cycle 2 – Day 1, 8, 15 and 22	400 mg QD: 1st Cycle of Exposure – Day 1, 8, 15 and 22
400 mg QD	Cycle 3 – Day 1, 8, 15 and 22	400 mg QD: 2 nd Cycle of Exposure – Day 1, 8, 15 and 22
300 mg BID	Cycle 4 – Day 1, 8, 15 and 22	300 mg BID: 1 st Cycle of Exposure – Day 1, 8, 15 and 22
300 mg BID	Cycle 5 – Day 1, 8, 15 and 22	300 mg BID: 2 nd Cycle of Exposure – Day 1, 8, 15 and 22

Note: Visits occurred at and after the visit where dose reduction occurred will not be mapped.

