5.5.2 Dose Limiting Toxicity (DLT)

The DLT definition is described in section 4.2 of the protocol. A patient data listing will be provided for all DLTs, if any.

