5.5.7 Vital Signs and Body Weight

Vital signs include blood pressures (BP), pulse, temperature and respiratory rate and body weight are measured at visits specified in the Schedule of assessments (Table 3 and Table 6).

The observed values and change from baseline values will be summarized by visit for each starting dose and overall.

The following ranges will be used to classified the BP and pulse measurements as Low/Normal/High:

- Systolic blood pressure (SBP): 90 to 140 mmHg, inclusive
- Diastolic blood pressure (DBP): 60 to 80 mmHg, inclusive
- Pulse: 50 to 100 bpm, inclusive

Shift from baseline tables will be produced by using the above criteria and the maximum post-baseline values.

Descriptive statistics tables will be generated for the vital sign measurements taken during the main and LTE period.

Patient data listings will be provided patients with out-of-range SBP, DBP or pulse results at any visits.

5.5.8 12-Lead ECG

Single ECG assessment is performed at the Screening, End of Study, Early Withdrawal and Unscheduled visit. Triplicate ECG assessments are performed at pre-dose and at 2 hours post-dose (+/- 15 minutes) on the first day of dosing at each new dose level. For patients continue into a new cycle at the prior dose level, ECG is not required.

The ECG parameters include: heart rate, QT interval, P-R interval, RR interval, QRS duration, QTcF interval and overall ECG assessments (normal, abnormal – not clinically significant (NCS) and abnormal – clinically significant (CS)).

For triplicate ECG assessments, the average of the three numerical values and the worst of the three overall ECG assessments will be used for the summary statistics.

For the numerical values, observed and change from baseline will be summarized by descriptive statistics.

For overall ECG assessments, shift from baseline tables will be for the worst post-baseline assessments.

Descriptive statistics tables will be generated for data collected during the main and LTE period.

A patient data listing will be provided for patients with abnormal CS ECG assessments at any visits.

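### Part A SAP: vital signs are set by starting dose, worst-value laboratory and ECG tables have no dose-level rule, DLTs are only listed, and none of this is declared as a change from the protocol

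*SAP*

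**What the plan says.** **Protocol.** Section 10.10 asks for qualitative Part A safety data per dose level, bounded by the dates of that level; its opening sentence covers TEAEs, laboratory tests, rescue use and vital signs. Section 10.10.3 repeats the rule for vital signs, with descriptive statistics reported "separately for each dosing level, using the time boundaries for that level in Part A". Section 10.10.4 adds: "The percentage of patients with a DLT will be summarized at each dosing level, overall for Part A, and overall for Part B".

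**Part A SAP.** Section 5.5 sets the default: "The summary statistics for the main period will be done by starting dose and overall for all study visits". The sentence does not end there; the grouping in full is "by starting dose and overall for all study visits and by cycle of exposure (as appropriate), unless specified otherwise". Section 3.4.4 defines cycles of exposure, and a last on-treatment value, within each dose level, but notes: "Visits occurred at and after the visit where dose reduction occurred will not be mapped". For vital signs, 5.5.7 says: "The observed values and change from baseline values will be summarized by visit for each starting dose and overall". For DLTs, 5.5.2 says: "A patient data listing will be provided for all DLTs, if any". Sections 5.5.6 and 5.5.8 plan shift tables, post-baseline maximum and minimum values, liver-threshold frequencies and worst-ECG shifts without saying how they are split by dose. Section 3.3.1 attributes responses, AEs, bleeding events and medications to a dose level, but not laboratory, vital-sign or ECG values. Section 4.5, which lists changes from the protocol, mentions none of this.

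**The concern.** Part A's objectives are to characterize safety at up to four dose levels and to identify a dose regimen for later studies. Its patients change dose during the main period. A starting-dose column is therefore a mixture of doses for anyone who escalates. A worst-value table takes one value per patient from the whole main period, so a peak ALT, an out-of-range blood pressure or an abnormal ECG reached at a higher dose is counted under a lower one. That flattens any dose relation in these measurements. The DLT percentage per dose level, the most direct dose-level safety summary in an escalation study, is not planned as a table at all.

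**Working it through.** The plan states no figure to reproduce here. The check compares the texts and then sizes the exposure concerned.

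**1. Which outputs lack a dose-level table**

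| Output | Protocol | Part A SAP |
|---|---|---|
| Vital signs | By dosing level within its dates (10.10.3) | By visit, starting dose and overall (5.5.7) |
| DLT | Percentage by dosing level and overall (10.10.4) | Listing only (5.5.2) |
| Laboratory shift tables | General dose-level rule (10.10); 10.10.2 asks for each time point, and for exploring dose against laboratory changes if any are seen | No dose rule (5.5.6) |
| Laboratory maximum/minimum, liver thresholds | General rule (10.10) only | No dose rule (5.5.6) |
| Worst ECG | No ECG table specified | No dose rule (5.5.8) |

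Where a SAP subsection is silent, the 5.5 default applies, which is starting dose.

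**2. What the cycle-of-exposure summaries can supply**

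They are by dose level, but with four limits:

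- They apply only as appropriate, and the SAP does not say to which tables.
- They consist of individual visits plus a last value. They give no worst value per dose level, so they cannot replace the shift, extreme-value or liver tables.
- They place Day 1 of a new dose under the new dose (the 3.4.4 example maps Cycle 2 Day 1 to 400 mg QD), yet Day 1 assessments are taken before dosing (SAP Table 4, footnote 13). Under versions 8 to 14, scheduled on-treatment chemistry falls only on Day 1 of each cycle and on Day 169. For a patient escalating each cycle, the one scheduled ALT filed under 400 mg QD precedes the first 400 mg QD dose. The SAP's own response examples in 5.4.1 credit Cycle 2 Day 1 to the preceding dose.
- Visits at and after a dose reduction are not mapped.

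**3. Size**

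Inputs: the dosing tables in protocol 4.1 and SAP 2.2 (4-week cycles), and the rule in protocol 4.1 that a patient who reaches 400 mg BID stays on it for 24 weeks. Case: a patient who escalates at every cycle.

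Share = weeks at 400 mg BID / total main-period weeks.

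| Starting dose | 24-week table | 24 weeks at 400 mg BID | Version 7 (12 weeks) |
|---|---|---|---|
| 200 mg QD | 12/24 = 50% | 24/(12+24) = 67% | 0/12 = 0% |
| 400 mg QD | 16/24 = 67% | 24/(8+24) = 75% | 4/12 = 33% |
| 300 mg BID | 20/24 = 83% | 24/(4+24) = 86% | 8/12 = 67% |

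Patients who start at 400 mg BID have no exposure filed under a lower label.

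**The case against.** The strongest reply is that the SAP does provide for dose level. The 5.5 default names cycle of exposure next to starting dose, and 3.4.4 makes that a dose-level grouping. AEs, Grade 2 or higher bleeding and rescue use are tabulated by dose level. A laboratory or ECG abnormality that causes symptoms, or a change in study drug or other therapy, is recorded as an AE (protocol 11.5.1) and so reaches a dose-level table. Safety listings show dose level, and with about 60 patients they can be read. The table shells are in a separate document, so the actual columns cannot be seen. Protocol 10.12 lets the SAP supersede the protocol's methods. Starting-dose tables are also a legitimate grouping, because each patient appears once.

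Much of this stands, and it rules out several stronger readings:

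- A reader might infer that findings at 400 mg BID are reported only under lower doses. The by-dose AE tables, the listings and the cycle-of-exposure summaries contradict that.
- A reader might infer that the least tolerant patients disappear from the by-dose view. Only visits at and after the reduction go unmapped; their earlier higher-dose visits stay mapped, and all scheduled visits remain in the study-visit summaries.
- A reader might infer that every affected table breaches a specific protocol instruction. The explicit conflicts are vital signs and the DLT percentage. The protocol's laboratory section sets no dose split for routine summaries, and its statistical section specifies no ECG table.

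The reply does not fill the gap. No subsection supplies a worst value per dose level, and a right to supersede the protocol does not explain why 4.5 is silent.

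**Conclusion.** The point holds in a limited form. Vital signs and the DLT percentage depart from explicit protocol text without being declared. The laboratory shift, maximum/minimum, liver-threshold and worst-ECG tables have no dose-level attribution and fall to the starting-dose default. The cycle-of-exposure summaries only partly make up for this.

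For patients who escalate every cycle, 50-83% of main-period exposure on the 24-week table, 67-86% with 24 weeks at 400 mg BID, and 0-67% under version 7 is at 400 mg BID but labelled with a lower starting dose. It would be tempting to read these as the share of abnormalities arising at 400 mg BID. The documents do not support that: it needs risk to be even over time, and a worst-value table counts each patient once. Responders do not escalate, so their shares are lower. The number of patients who started below 400 mg BID is not given; the dosing table shows cohorts of 3-6 or at most 6.

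Two assumptions remain. Silent subsections are taken to follow the 5.5 default. The SAP was written on protocol version 14, and the protocol text compared is amendment 16, whose change table lists no change to the statistical section. The amendment 15 change table is incomplete in the text available, so it cannot be checked in full.

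**What to change.** - In SAP 3.3.1, add laboratory, vital-sign and ECG values, attributed to the dose level received before the assessment. Pre-dose Day 1 samples go to the preceding dose level and post-dose samples to the dose just taken. The AE onset rule should not be used, because it would credit pre-dose Day 1 samples to the new dose.
- Produce the vital-sign summaries and the shift, maximum/minimum, liver-threshold and worst-ECG tables by dose level, taking the worst value within that level's dates, and overall. Keep the starting-dose tables as supportive.
- Map visits after a dose reduction to the dose actually taken.
- Tabulate DLT n (%) by dose level and overall.
- List any remaining departure from the protocol in SAP 4.5.

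No new data are needed, since dose-level start and stop dates are already derived in SAP 5.3.2. The Part B SAP (1.1) says that a Part A report has been prepared, so supplementary tables and a declared change would be enough. The cost is more tables.

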5.5.1 Adverse Events

TEAEs will be attributed to the dose level where the AE start date is on or after the start date of that dose level and before the next dose level if applicable. TEAEs started after date of last study drug dosing will be attributed to the last dose level received.

The following summaries of adverse events will be provided:

	All patients		
	(By Dose Level		
	and Overall)	LTE patients	
		Main + LTE	
Summary	Main Period	Period	LTE Period
Overview of adverse event profile: Treatment			
emergent adverse events	X	X	X
TEAEs by primary SOC and PT (number of patients,			
number of events and event rate)	X	X	Х
TEAEs reported in >=5% patients by PT in descending			
order (number of patients)	Χ		
TEAE leading to study drug discontinuation by			
primary SOC and PT (number of patients)	X	X	X
TEAE leading to death by primary SOC and PT			
(number of patients)	X		
Treatment emergent SAE by primary SOC and PT			
(number of patients)	X	X	X
TEAEs by the maximum intensity, primary SOC and			
PT (number of patients)	X	X	X
Related TEAEs by primary SOC and PT (number of			
patients, number of events and event rate)	X	X	Х
Related TEAEs by the maximum intensity grade,			
primary SOC and PT (number of patients)	X	X	Х
TEAEs intensity Grade>=3 by primary SOC and PT			
(number of patients)	X	X	Х
Bleeding events by primary SOC and PT (number of	X (for overall		
patients, number of events and event rate)	only)	X	Х
Related bleeding events by primary SOC and PT			
(number of patients, number of events and event	X (for overall		
rate)	only)	X	Х
Bleeding events (Intensity Grade 2 or higher) by			
primary SOC and PT (number of patients, number of			
events and event rate)	X	X	Х
Related bleeding events (Intensity Grade 2 or higher)			
by primary SOC and PT (number of patients, number			
of events and event rate)	X	X	X
TEAEs by primary SOC and PT and by age group (<65,			
>=65 years) (number of patients)	X		

	All patients		
	(By Dose Level		
	and Overall)	LTE pati	ents
		Main + LTE	
Summary	Main Period	Period	LTE Period
TEAEs by primary SOC and PT and interquartile age			
group (number of patients)	X		
TEAEs by primary SOC and PT and by gender (male,			
female) (number of patients)	X		
TEAEs by primary SOC and PT and by concomitant			
ITP medications (No concomitant ITP medication,			
Corticosteroids alone, TPO-RA alone, Corticosteroids			
+ TPO-RA) (number of patients)	X		

[&]quot;X" represents a summary table will be provided.

Patients with multiple events within a particular primary SOC or PT within each dose level/study period will be counted once within that dose level/study period. Adverse events will be sorted by primary SOC internationally agreed order and within each primary SOC, by overall descending frequency of PT. For primary SOC or PT with tied frequency, they will be sorted in alphabetical order.

Event rate is calculated as number of patients with an event divided by total patient year during the respective observation period.

For by maximum severity tables, patients with multiple events within a particular primary SOC or PT will be counted once under the maximum intensity grade.

The following AE tables will be created for the "overall" group:

- Pre-treatment AEs by primary SOC and PT (number of patients)
- Post-treatment AEs by primary SOC and PT (number of patients)

Patient data listings will be generated for:

- AEs
- SAEs
- AE leading to study drug discontinuation

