3.4 Analysis Timepoints and Definitions

3.4.1 Observation Period

The observation period will be divided into 3 segments:

- 1) The **pre-treatment period** is defined as the period to the date of first dose of study drug.
- 2) The **on-treatment period** is defined as the period from the first dose of study drug to the last dose of study drug + 1. The on-treatment period includes the main treatment period and the LTE period.
 - Main on-treatment period is defined as from the date of first dose of study drug
 - to the date of the last dose of study drug + 1, if the patient did not enter LTE.
 - to the date before the first dose of study drug during LTE, if the patient entered LTE.
 Date of first dose in LTE is based on the date of dosing reported on C1D1_LTE Study
 Drug Administration eCRF.
- 3) The **post-treatment period** is defined as the period from the end of the on-treatment period. That is, the 4-week post treatment follow up period per protocol.

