3.4.2 Analysis Period

There are primarily 3 analysis periods for safety analyses:

- 1) Main period is
 - Main on-treatment period + FU, if the patient did not enter LTE
 - Main on-treatment period only, if the patient entered LTE
- 2) LTE period is LTE on-treatment period + FU
- 3) Main and LTE period combined, if the patient entered LTEs

Efficacy analyses will be based on on-treatment period (i.e., up to end of treatment +1 day), with the exception of descriptive analyses which will include post-treatment follow up visits.

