5.3.2 Actual Total Cumulative Dose (mg)

Actual total cumulative dose in main treatment period (mg) = Sum of (Dose Level $_i$ (x2 if BID) x actual duration of study drug exposure in main treatment period for Dose Level $_i$ – total # of doses missed in Dose Level $_i$ during main treatment period))

Actual duration of study drug exposure in main treatment period for each dose level will be based on (Date of last dose in Dose Level $_i$ – Date of first dose in Dose Level $_i$) + 1, regardless of unplanned intermittent interruption

For patients who only had one dose level, the actual duration of Dose Level_i is the same as duration of study drug exposure in Section 5.3.1.

For patients with more than one dose levels:

- Date of first dose for the starting dose level is date of first dose taken at Cycle 1 Day 1.
- Date of first dose for the subsequence dose levels is the date of dosing reported on the Study Drug Administration eCRF where a dose adjustment was made. If the date of dosing is missing, then the date of visit where dose adjustment made will be used.
- Date of last dose for Dose Level_i is the date of first dose of the next dose level -1.
- Date of last dose for the last dose level is the date of last dose reported on the End of Study form.

Actual total cumulative dose in LTE treatment period (mg) = 400 mg x2 if BID x actual duration of study drug exposure in LTE treatment period – total # of doses missed in LTE treatment period)

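### The Part A adverse event rate divides patients, each counted once, by total patient-years, so it is neither events per patient-year nor a first-event rate

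*SAP*

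**What the plan says.** SAP Part A section 5.5.1 defines the rate in one sentence: "Event rate is calculated as number of patients with an event divided by total patient year during the respective observation period". Just before it comes the counting rule: a patient with several events in the same class or term "will be counted once within that dose level/study period". Nothing stops a patient's time at the first event.

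The table of planned summaries in the same section asks for the number of patients, "number of events and event rate" in six rows: TEAEs, related TEAEs, bleeding events, related bleeding events, Grade 2 or higher bleeding, and related Grade 2 or higher bleeding. For the main period, four of the six are by dose level and overall; all bleeding and related bleeding are overall only.

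On post-treatment events, section 5.5.1 says "TEAEs started after date of last study drug dosing will be attributed to the last dose level received". Section 3.4.2 defines the main safety period as "Main on-treatment period + FU, if the patient did not enter LTE", and the LTE period also includes follow-up. No section defines patient-years by dose level for this rate.

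**The concern.** The numerator is a count of patients and the denominator is all their time. Events per patient-year would count every event. A first-event rate would stop each patient's time at the first event. The planned quantity does neither, yet it carries the name event rate and stands next to the number of events.

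Two things are at stake. For recurrent events, a patient with many events adds one to the numerator. For common events, the value depends on how long patients stay at a level, and that differs by design: patients without a platelet response may move up after 28 days, while a patient can spend 24 weeks at one level (SAP Part A section 2.2, Table 2; protocol section 4.1). Two levels with the same underlying risk would then show different rates. Characterizing safety across dose levels is a stated Part A objective.

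**Working it through.** The documents give no expected rate and no patient-year total, so there is no figure to reproduce. The 4 and 24 weeks come from the dosing tables; the hazards and event patterns below are assumptions.

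**Exposure length.** With constant hazard h per patient-year and time T at the level, the expected proportion of patients with an event is 1 − exp(−hT). The SAP rate is therefore (1 − exp(−hT))/T. For 4 weeks, T = 28/365.25 = 0.0767 years; for 24 weeks, T = 168/365.25 = 0.460 years.

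| Hazard h | Patients affected in 24 weeks | SAP rate, 4 weeks | SAP rate, 24 weeks | Ratio |
|---|---|---|---|---|
| 0.1 | 4.5% | 0.0996 | 0.0977 | 0.981 |
| 0.25 | 11% | 0.248 | 0.236 | 0.954 |
| 0.5 | 21% | 0.491 | 0.447 | 0.911 |
| 1.0 | 37% | 0.963 | 0.802 | 0.833 |
| 2.0 | 60% | 1.854 | 1.308 | 0.705 |

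Patients divided by patient-years to first event returns h at both durations, so the difference comes from the formula alone.

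**Distance from a first-event rate.** If p is the proportion of patients with an event, the SAP rate divided by the first-event rate is p/(−ln(1 − p)). This is 0.97 at p = 5%, 0.95 at 10%, 0.84 at 30%, 0.72 at 50% and 0.58 at 70%.

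**Recurrent events.** Assume 10 patients treated for 168 days, of whom 4 have 3 events each, the first on day 28. Total time is 10 × 168/365.25 = 4.60 patient-years. Time to first event is (6 × 168 + 4 × 28)/365.25 = 3.07 patient-years.

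- SAP rate: 4/4.60 = 0.87
- Events per patient-year: 12/4.60 = 2.61
- First-event rate: 4/3.07 = 1.30

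**Sampling error.** With 4 patients in 4.60 patient-years, the exact Poisson 95% interval for 0.87 is 0.24 to 2.23. At these numbers, chance is larger than most of the biases in the table.

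**The case against.** The SAP states the formula openly, so nothing is hidden. Patients per total exposure is sometimes used as an exposure-adjusted incidence and is close to a first-event rate for rare terms. Patient and event counts are shown beside it, and the table shells, which may carry clearer labels, are in a separate document. Section 3.8 plans no hypothesis testing, the escalation rules do not use the rate, and protocol section 10.10.1 asks only for number and percent. Dose levels are sequential within patients and non-responders escalate, so dose columns would not be directly comparable even with a correct rate.

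All of that stands, and it sets the severity. It does not make the quantity an event rate, and the approximation fails for the any-TEAE rows and common terms, where a rate would most likely be read.

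A reader might go further and infer that follow-up events are counted at the last dose level while follow-up time is left out. Section 5.3.2 does say "Date of last dose for the last dose level is the date of last dose reported on the End of Study form". On that reading, and with equal risk on and off drug, the rate would be inflated by (dose weeks + follow-up weeks)/dose weeks: 28/24 = 1.17 for 24 + 4 weeks, and up to 16/4 = 4.0 for a version 7.0 patient with 4 weeks at the last level and 12 weeks of follow-up. The documents do not support this as a stated error. Section 5.3.2 defines durations for cumulative dose and is never named as the rate's denominator. Section 3.4.1 lists the post-treatment period among the observation-period segments, and section 3.4.2 puts follow-up in the safety periods. The dose-level denominator is undefined, not defined wrongly.

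Nor does the gloss in section 3.4.1, "That is, the 4-week post treatment follow up period per protocol", cut off data for version 7.0 patients: the period is defined as starting when the on-treatment period ends, and section 3.4.3 lists their follow-up visits to Day 169.

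**Conclusion.** Wrong as written, severity minor. The formula yields neither of the two quantities its name could mean. Under an assumed constant hazard, 24 weeks at a level reads 2% to 29% lower than 4 weeks at equal risk, for hazards of 0.1 to 2.0 per patient-year; rare terms are barely affected. The scope is the six summaries that carry a rate, four of them by dose level. The SAE, discontinuation, Grade 3 or higher and maximum-intensity tables carry none, and the Part B adverse event tables report number and percent only.

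Follow-up time at the last dose level needs a rule, because post-treatment events are assigned there. The factors of 1.17 to 4.0 describe only what would follow if that time were omitted; they are not a finding about the plan. How many patients they could apply to is not in the documents, and pooling with other patients would dilute them.

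**What to change.** Define the rate in section 5.5.1 in one of two ways and label it to match:

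- number of events divided by patient-years; or
- patients with at least one event divided by patient-years to first event, censored at the end of the period to which events are attributed.

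The first fits the current name and the event count beside it.

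In the same edit, refer to the section 3.4.2 analysis periods instead of the observation period. For the last dose level, either add each patient's actual observed follow-up time to the denominator or leave post-treatment events out of the dose-level rate. A nominal 4 or 12 weeks should not be added. It would be wrong for early withdrawals, for version 7.0 patients who reconsented to 24 weeks (protocol Appendix 10, version 8 history), and for earlier completers who later entered the LTE (SAP Part A section 2.2).

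The cost is a short SAP clarification and a small programming change. SAP Part B section 1.1 says that a Part A study report has been prepared, so the six summaries need a re-run, or a footnote naming the current quantity as patients with an event per total patient-years. After a re-run, rates for common or recurrent events will be higher.
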